## 4.4.5 Subgroup Analyses

Subgroup analyses will be provided in forest plots for the following endpoints:

- Change from baseline in BCVA score averaged over Week 36 and Week 40
- Change from baseline in CPT at Week 36

Subgroups will be Age (< 65 years, 65 to <75 years,  $\geq$  75 years) and Sex (male, female). In addition subgroups may be analyzed according to number of anti-VEGF injections performed before randomization (<5,  $\geq$ 5), baseline BCVA (< 74 letters vs.  $\geq$  74 letters). The analyses will follow the same methods (except in the case of baseline BCVA subgroup the baseline covariate consisting of the BCVA stratification factor will be removed) as for these endpoints in the overall analysis but will be done for each subgroup separately.

#### 4.5 PHARMACOKINETIC ANALYSES

Individual and mean serum ranibizumab concentration versus time data will be tabulated and plotted by treatment group for all patients in the Pharmacokinetic Population and Pharmacokinetic-Evaluable Population. In a subset of patients in the PDS 100 mg/mL group with more intensive sampling (at selected sites), the serum pharmacokinetics of ranibizumab will be summarized by estimating total exposure (area under the concentration-time curve [AUC]), maximum serum concentration (Cmax), and half-life (t1/2) of drug delivered from the implant after PDS implant insertion. Estimates for these parameters will be tabulated and summarized (mean, standard deviation, coefficient of variation, median, and minimum and maximum). Inter-patient variability will be evaluated.

Exploratory PK analyses to evaluate potential relationships between drug exposure and efficacy of the PDS will be performed. Additional PK analyses will be conducted as appropriate.

#### 4.6 EXPLORATORY BIOMARKER ANALYSES

Pharmacodynamic (PD) biomarker analyses will be focused primarily on, but not limited to, the change in free-VEGF or other angiogenesis-related biomarker concentrations (absolute or percent change as appropriate) over time and analyzed based on the Biomarker Analysis Population. The data will be analyzed in the context of ranibizumab pharmacokinetics, using a longitudinal model approach, to gain an understanding of the relationship between ranibizumab concentrations and target modulation. Results will be summarized descriptively.

Additional analyses will be performed, as deemed appropriate, to explore biomarkers that are associated with progression to a more severe disease, acquired resistance to ranibizumab, and susceptibility to developing AEs, can provide evidence of ranibizumab activity, or can increase the knowledge and understanding of disease biology. Prognostic biomarker analyses will include all patients for which biomarker assessments were made during randomization ("baseline"). Baseline values will be used to evaluate prognostic biomarkers in the context of efficacy, PK, safety, and/or immunogenicity endpoints. Results will be summarized descriptively.

#### 4.7 SAFETY ANALYSES

The safety analyses will be performed on the Safety Population (described in Section 4.1.6).

Safety will mainly be assessed through descriptive summaries of AEs, ocular assessments, and anti-drug antibodies (ADAs) to ranibizumab. Clinically significant laboratory abnormalities and clinically significant vital sign abnormalities will be reported as AEs and evaluated as part of the AE assessments.

At the time of the primary analysis, safety data will be summarized based on the complete Week 40 data in the Safety Population. In addition, ongoing safety data (from first treatment up to a single specified clinical cutoff date) in the Safety Population will also be summarized. Such results will be reported with, but separate from, the 40-week study results to provide additional safety information.

At the time of the final analysis, safety summaries will be produced based on cumulative Week 96 data in the Safety Population. Due to the addition of several final study visit scenarios specified in the Protocol Version 4 in order to provide flexibility and assure appropriate patient care in response to the COVID-19 public health emergency, safety data will be available for some patients beyond Week 96. Post-Week 96 data will not be included in the safety summaries and will be provided separately in a listing.

#### 4.7.1 Adverse Events

All verbatim AE terms will be coded using the latest version of Medical Dictionary for Regulatory Activities (MedDRA).

For safety analyses, unless otherwise specified, only treatment-emergent AEs will be included in the analyses. Treatment-emergent AEs will be defined as any new AEs reported or any worsening of an existing condition on or after the surgical insertion of the implant or the first intravitreal ranibizumab injection post randomization through the completion of the study or until a patient discontinues prematurely. Adverse events with missing onset date will be considered to be treatment emergent. Adverse events with partially missing onset date will also be included as treatment emergent when the month (if it was recorded) and the year occur on or later than the month and year of the study treatment start date.

Frequency tables, including patient incidence rates by treatment group, will be provided for the events listed below. For ocular AEs, events in the study eye and fellow eye will be summarized separately.

- Ocular AEs and serious adverse events (SAEs)
- Non-ocular AEs and SAEs
- Adverse events of special interest (AESI) defined as follows:
  - An AE considered to be sight threatening (see Section 5.2.3 of the Protocol)
  - Cases of potential drug-induced liver injury that include elevated alanine aminotransferase (ALT) or aspartate aminotransferase (AST) in combination with either an elevated bilirubin or clinical jaundice, as defined by Hy's Law (see Section 5.3.5.6 of the Protocol)
  - Suspected transmission of an infectious agent by the study drug
  - Ocular AESIs (formerly adverse events potentially related to PDS) defined as:
    - Vitreous hemorrhage
    - o Endophthalmitis
    - Retinal detachment
    - Conjunctival retraction
    - Conjunctival erosion
    - Conjunctival bleb or conjunctival filtering bleb leak
    - Hyphema
    - Cataract (includes Preferred Terms cataract, cataract nuclear, cataract cortical, and cataract subcapsular)
    - Device dislocation (added in Protocol v 5)
- AEs leading to discontinuation of study treatment
- Treatment related Ocular AEs and SAEs as determined by the Investigator
- Anti-Platelet Trialists Collaboration Events (APTCs) defined as:
- non-fatal stroke AEs defined by terms from the conditions associated with central nervous system haemorrhages and cerebrovascular accidents Standardized

- MedDRA Query (SMQ) (Narrow), ischaemic cerebrovascular conditions SMQ (Narrow), and haemorrhagic cerebrovascular conditions SMQ (Narrow) or
- non-fatal myocardial infarction AEs defined by terms from the myocardial infarction SMQ (Narrow) or
- vascular death (including deaths of unknown cause)

Of note, vitreous hemorrhage data will be presented by the functional grading scale for vitreous hemorrhage (see Study GR40458 Study Protocol Appendix 8) which incorporates impact of vitreous hemorrhage on patient's BCVA. All vitreous hemorrhage data will be presented however for key analyses the focus will be on Grades 3 and 4 as these are clinically relevant when discussing vitreous hemorrhage.

A subgroup analysis of cataract incidence will be performed by baseline lens status subgroup (phakic vs pseudophakic), as in the Primary CSR Section 3.11.8.

In addition, the rates of intraocular inflammation AEs will be analyzed as in the Primary CSR Section 6.3.5.2.1, based on selected PTs according to the Standardization of Uveitis Nomenclature (SUN) (Jabs et al. 2005). Intraocular inflammation will be defined as anterior uveitis (included iritis, iridocycltis, anterior cyclytis, anterior channel cell, flare, and inflammation); intermediate uveitis (included pars planitis, posterior cyclitis, hyalitis, vitritis, and vitreous haze); posterior uveitis (included choroiditis, chorioretinitis, retinochoroiditis, retinitis, neuroretinitis, and retinal vasculitis); and events which were not otherwise specified (included eye inflammation, uveitis, post procedural inflammation, incision site inflammation, inflammation of wound, and ocular vasculitis). Endophthalmitis, while included in the SUN criteria for intraocular inflammation, will be analyzed separately as an AESI.

Adverse events (AEs) of endophthalmitis will additionally be summarized as incidence rates by treatment group on a per study treatment intervention basis (total number of endophthalmitis AEs divided by the total number of interventions in the study eye. Interventions in the intravitreal group include intravitreal ranibizumab injections. Interventions in the PDS 100 mg/ml group include implantation, PDS refill-exchange procedure, and supplementary ranibizumab treatment in the study eye.

Frequency tables including patient incidence rates will also be generated by treatment group and by onset of events using the following time windows relative to first dose or implant surgery:

- ≤Week 4 (up to the end of Week 4 visit window, ≤37 days) (post-operative period)
- >Week 4 (>37 days) (follow-up period)

for the following AEs:

- Ocular AEs and SAEs in the study eye
- Ocular AESIs.

A listing of patients who died during the study will be provided.

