# 5.1.2.2 Cataract

Cataract may be a clinically relevant event with possible outcome of visual loss. Patients receiving intravitreal injections are at risk for the development of traumatic cataract. During the intravitreal injection, any direct trauma to the lens by the needle touching the lens could result in traumatic cataract.

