#### 5.2.3 Adverse Events of Special Interest (Immediately Reportable to the Sponsor)

Adverse events of special interest are required to be reported by the investigator to the Sponsor immediately (i.e., no more than 24 hours after learning of the event; see Section 5.4.2 for reporting instructions). Adverse events of special interest for this study are as follows:

- Cases of potential drug-induced liver injury that include an elevated ALT or AST in combination with either an elevated bilirubin or clinical jaundice, as defined by Hy's Law (see Section 5.3.5.6)
- Suspected transmission of an infectious agent by the study drug, as defined below

Any organism, virus, or infectious particle (e.g., prion protein transmitting transmissible spongiform encephalopathy), pathogenic or non-pathogenic, is considered an infectious agent. A transmission of an infectious agent may be suspected from clinical symptoms or laboratory findings that indicate an infection in a patient exposed to a medicinal product. This term applies only when a contamination of the study drug is suspected.

- Sight-threatening adverse events: an adverse event is considered to be sight threatening if it is a serious adverse event (as defined in Section 5.2.2) and it meets one or more of the following criteria:
  - The adverse event causes a decrease of ≥30 letters in BCVA (compared with the last assessment of VA prior to the most recent treatment) lasting more than 1 hour.

- The adverse event requires surgical intervention (i.e., conventional surgery, vitrectomy, vitreous tap, or biopsy with intravitreal injection of anti-infective medications, or laser or retinal cryopexy with gas) to prevent permanent loss of sight.
- The adverse event is associated with severe intraocular inflammation (e.g., endophthalmitis, 4+ anterior chamber cell/flare or 4+ cells in the vitreous; see Appendix 7 for intraocular inflammation grading scales).

Note: Adverse events should be reported, listing the underlying cause (if known) of the event as the primary event term (see Section 5.3.5.2).

- Ocular adverse events of special interest, defined as any of the events listed below, regardless of whether they occur in the study eye or the fellow eye, in a patient randomized to the PDS arm or the intravitreal arm, or the AE causality:
  - Vitreous hemorrhage
  - Endophthalmitis
  - Retinal detachment
  - Conjunctival retraction
  - Conjunctival erosion

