#### 6.5.1 Adverse Events

All verbatim adverse event terms will be mapped to MedDRA thesaurus terms, and their incidence will be summarized by treatment arm.

Treatment-emergent adverse events will be defined as events beginning at the surgical insertion of the implant or at the first intravitreal ranibizumab 0.5 mg injection through the

**Port Delivery System with Ranibizumab—F. Hoffmann-La Roche Ltd.** 109/Protocol GR40548, Version 5

completion of the study or until a patient discontinues prematurely. Adverse events will be tabulated by body system and preferred term. All adverse events, serious adverse events, deaths, adverse events leading to discontinuation of study treatment, adverse events of special interest, and adverse events judged to be related to study treatment or procedure will be summarized overall and by the adverse event onset day ( $\leq$  37 days vs. > 37 days). Separate summaries will be prepared for non-ocular and ocular adverse events, with events in the study eye and fellow eye summarized separately.

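### The SAP's four-term list for the cataract AESI may leave out traumatic cataract, which the protocol's definition covers

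*SAP*

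**What the plan says.** Protocol 5.2.3 lists cataract among the ocular AESIs with no restriction to particular preferred terms. The list applies "regardless of whether they occur in the study eye or the fellow eye, in a patient randomized to the PDS arm or the intravitreal arm", and whatever the assessed causality. Sites must report these events to the sponsor within 24 hours.

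Protocol 5.1.2.2 describes the mechanism for injections: "Patients receiving intravitreal injections are at risk for the development of traumatic cataract", because "any direct trauma to the lens by the needle touching the lens could result in traumatic cataract". Protocol 5.1 separately lists new or worsening cataract, without reference to trauma, among the possible safety issues of intravitreal ranibizumab.

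SAP 4.7.1 gives the analysis definition. Under the ocular AESIs it has "Cataract (includes Preferred Terms cataract, cataract nuclear, cataract cortical, and cataract subcapsular"). On coding it says only that "All verbatim AE terms will be coded using the latest version of Medical Dictionary for Regulatory Activities (MedDRA").

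The same section plans three outputs that could draw on this list: the AESI frequency table, the ocular-AESI table split at 37 days after first dose or surgery, and cataract incidence by baseline lens status. For the last of these it refers to Section 3.11.8 of the Primary CSR and does not restate the terms. SAP Section 1 says that the SAP takes precedence over the protocol's analysis plan.

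**The concern.** The analysis list is narrower on its face than the AESI it is meant to implement. Its terms are either unspecified (cataract) or describe where in the lens the opacity lies (nuclear, cortical, subcapsular). None refers to trauma, yet trauma is the mechanism that Protocol 5.1.2.2 sets out. A site could report a traumatic cataract promptly as an AESI, as the protocol requires, and the event could then fail to enter the cataract AESI row.

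The arms also differ in their procedures. Control patients are scheduled for repeated injections. Implant patients have one insertion operation, refill-exchanges and, if criteria are met, supplemental injections. A definition that drops a procedure-related form of cataract could therefore affect the two arms unequally in the one row where a reader looks for the cataract comparison.

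**Working it through.** The plan gives no cataract count or rate, so there is no figure to reproduce. The check is a comparison of texts, followed by an illustration of scale.

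**Scope.** The protocol AESI covers any cataract, either eye, either arm, any causality. The SAP AESI names four preferred terms. Traumatic cataract is inside the first and is not named in the second.

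**What an omission requires.** All three of these must hold:

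1. The four terms are the complete list. The SAP word is *includes*, which leaves this open, although the entry sits under a heading that defines the ocular AESIs and is the only cataract list given.
2. A traumatic cataract codes to a preferred term other than the four. The documents do not say.
3. At least one such event occurs in a patient with no listed-term cataract. The documents give no information.

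If any one fails, the undercount is zero.

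**Where the event would and would not appear, if all three hold.**

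| Output | Traumatic cataract outside the list |
|---|---|
| Cataract AESI row | Missing |
| Ocular-AESI onset table (37-day split) | Missing |
| Cataract by lens status | Unknown; terms not restated in the SAP |
| All ocular AEs and SAEs, by eye | Present |
| Study-eye ocular AE and SAE onset table | Present, if in the study eye |
| Treatment-related ocular AEs | Present, if judged related |
| Sight-threatening AESI | Present only if serious and meeting a further criterion in Protocol 5.2.3 |

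**Scale (illustration).** Inputs: 418 enrolled (Protocol 6.1) and 3:2 allocation. Realized arm sizes are not given, so these are approximations.

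- Intravitreal arm: 418 × 2/5 = 167.2, about 167. One patient = 1/167 = 0.60 percentage points.
- Implant arm: 418 × 3/5 = 250.8, about 251. One patient = 1/251 = 0.40 percentage points.
- Let r be the proportion of an arm's patients whose only cataract event is a traumatic one outside the list. Expected omissions are n × r. For an *assumed* r of 0% to 2%, this is 0 to 167.2 × 0.02 = 3.3 intravitreal patients and 0 to 250.8 × 0.02 = 5.0 implant patients.
- Each arm's AESI incidence falls by its own r, so the implant-minus-intravitreal difference shifts by r(intravitreal) − r(implant). It does not move if the two are equal. Over the assumed range it moves by anything from −2 to +2 points.

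**Direction.** Scheduled control injections run from Day 1 to Week 92 every 4 weeks: 92/4 + 1 = 24. Implant patients have one insertion, three scheduled refill-exchanges (Weeks 24, 48 and 72) and possible supplemental injections. The documents give no lens-trauma rate for any of these procedures, so the sign of the shift cannot be derived.

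**The case against.** The strongest reply is that nothing is shown to be lost. The list is introduced by *includes*, the coding of traumatic cataract is not stated, and the event remains visible elsewhere. SAP 4.7.1 tabulates "Ocular AEs and serious adverse events (SAEs") by eye and arm, and Protocol 6.5.1 says that "Adverse events will be tabulated by body system and preferred term". A traumatic cataract with its own term would therefore have its own row there. A serious case could also enter through "An AE considered to be sight threatening (see Section 5.2.3 of the Protocol"). SAP 4.7 describes the safety analysis as mainly descriptive, so no test depends on the grouped count.

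Most of this stands, and it rules out several stronger readings that a reader might infer:

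- *That cataract is undercounted.* This needs all three conditions in the check above, and the documents establish none of them.
- *That trauma is the only form of cataract the protocol links to injections.* Protocol 5.1 also names new or worsening cataract without that limit, so the traumatic form cannot be called the most informative one either.
- *That the event would vanish from the onset analysis.* Only the AESI version of that table is exposed. The study-eye ocular AE version would keep a study-eye event.
- *That it would drop out of the lens-status analysis.* The term set is in a CSR section not available here.
- *That a control-arm loss can be sized from a rate per injection.* No such rate is given. Control injections that are missed are not made up, and the lens-status subgroups include pseudophakic patients, who have no natural lens to injure.

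The reply does not remove the mismatch. The all-ocular-AE table lists terms separately, whereas the AESI row is the grouped cataract count. If the four terms are not exhaustive, that count cannot be reproduced from the SAP, and the same clarification is needed. The sight-threatening category catches only serious cases that meet an additional criterion.

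**Conclusion.** The concern holds as a mismatch of definitions with a possible, unquantified effect. SAP 4.7.1 groups the cataract AESI by four preferred terms, which is narrower than Protocol 5.2.3, and does not say where a traumatic cataract is counted. If such an event codes outside the four terms, the grouped AESI row and the ocular-AESI onset table would miss it, and the lens-status analysis might too. Overall ocular AE reporting would not.

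The effect may be nil. If it is not, each omitted patient is worth about 0.6 points in the intravitreal arm or 0.4 in the implant arm, assuming that the 418 patients split exactly 3:2. The 0% to 2% range is an assumption made for scale and comes from neither document. The direction of any effect on the arm comparison is unknown. This is worth settling because cataract is a designated AESI and the correction is small, not because a bias has been shown.

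**What to change.** In SAP 4.7.1, replace the four-term parenthesis with a definition: every preferred term, in the MedDRA version used, that denotes cataract under Protocol 5.2.3, explicitly including any traumatic cataract term. State that the resulting list is complete. Use that one list for the AESI table, the ocular-AESI onset table and the phakic/pseudophakic analysis.

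The cost is one SAP line and one programming list, applied to data already collected. Cataract counts may then differ slightly from those in the Primary CSR. A footnote giving the added terms and the number of patients they contribute in each arm would explain any difference.

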# 5.1.2.3 Intraocular Inflammation

Intraocular inflammation can range from a mild to severe inflammation of the eye with sequelae that may lead to vision loss. Inflammation can occur due to potential immunogenicity, in reaction to the active substance or its excipients, or in response to the invasive nature of the procedure. It is also hypothesized that intravitreal antibody formation may contribute to the development of intraocular inflammation; however, there is currently no evidence either from the published literature or from the postmarketing data to support this assertion. There is potential introduction of microorganisms during the injection procedure as described below in Section 5.1.2.5 (endophthalmitis).

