#### 5.3.5 Procedures for Recording Adverse Events

Investigators should use correct medical terminology/concepts when recording adverse events on the Adverse Event eCRF. Avoid colloquialisms and abbreviations.

Only one adverse event term should be recorded in the event field on the Adverse Event eCRF.

For the purposes of reporting events of infection and inflammation, the following terms and definitions should be used (see also Appendix 7 and Appendix 8):

• Iritis: the presence of inflammatory cells in the anterior chamber (trace or greater)

The presence of aqueous humor flare alone will not constitute iritis but should be documented as an anterior chamber flare for adverse event reporting purposes.

- Iridocyclitis: the presence of inflammatory cells in both the aqueous humor and vitreous (trace or greater)
- Vitritis: the presence of active inflammation in the vitreous, demonstrated by the presence of inflammatory cells (trace or greater)

Active inflammation in the vitreous should be clinically differentiated from cellular debris from prior episodes of inflammation, hemorrhage, or other causes.

• Endophthalmitis: diffuse intraocular inflammation predominantly involving the vitreous cavity but possibly also involving the anterior chamber, implying a suspected underlying infectious cause

A culture is required prior to initiating antibiotic treatment for presumed infectious endophthalmitis.

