Patients who are randomly allocated to the PDS 100 mg/ml arm will have the implant (pre-filled with 100 mg/mL ranibizumab) surgically inserted on Day 1, which must occur 1-7 days (inclusive) after randomization (i.e., randomization and Day 1 visit assessments cannot be performed on the same day) and no later than 28 days from the last intravitreal ranibizumab injection. After Day 1, patients in the implant arm will have scheduled safety visit assessments on Days 2 and 7 ( $\pm$ 2 days) and will receive implant refill-exchanges with 100 mg/mL ranibizumab Q24W at Week 24 ( $\pm$ 7 days), Week 48 ( $\pm$ 7 days), and Week 72 ( $\pm$ 7 days).

Patients who are randomly allocated to the intravitreal arm will receive 0.5 mg of ranibizumab intravitreal injections starting on Day 1, which is to be administered at the conclusion of the randomization visit (i.e., randomization and Day 1 visit assessments are performed on the same day). Patients will receive 0.5 mg ranibizumab, injected intravitreally Q4W (±7 days) from Day 1 until Week 92.

Patients randomized to the implant arm will be eligible for supplemental treatment with intravitreal ranibizumab (0.5 mg intravitreal injections of 10 mg/mL formulation) at Weeks 16 and 20 (after implant insertion) and at Weeks 40, 44, 64, 68, 88, and 92 if any of the following criteria are met in the study eye:

 Decrease of ≥15 letters from the best-recorded BCVA in the study, due to nAMD disease activity.

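### The SAP's intraocular inflammation rate includes two wound terms tied to a surgical incision that is study treatment only in the implant arm, and its anatomical split files iridocyclitis as anterior although the protocol's reporting definition includes vitreous cells

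*SAP*

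**What the plan says.** SAP 4.7.1 plans an analysis of IOI adverse event rates, carried over from the Primary CSR and "based on selected PTs according to the Standardization of Uveitis Nomenclature (SUN"). The terms fall into four groups: anterior, intermediate, posterior and not otherwise specified. Endophthalmitis is handled separately as an adverse event of special interest.

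- The fourth group is "events which were not otherwise specified (included eye inflammation, uveitis, post procedural inflammation, incision site inflammation, inflammation of wound, and ocular vasculitis").
- The first group is "anterior uveitis (included iritis, iridocycltis, anterior cyclytis, anterior channel cell, flare, and inflammation"). I read its second term as iridocyclitis. Vitritis is in the intermediate group.

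Protocol 5.3.5 governs how sites name these events: "For the purposes of reporting events of infection and inflammation, the following terms and definitions should be used". One of the definitions is "Iridocyclitis: the presence of inflammatory cells in both the aqueous humor and vitreous (trace or greater"). Iritis is reserved for anterior chamber cells and vitritis for vitreous cells. The same section allows only one term per event field.

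On exposure, SAP 2 says the implant is "surgically inserted on Day 1, which must occur 1-7 days (inclusive) after randomization", while the intravitreal arm receives injections every 4 weeks until Week 92. Protocol 4.4.1 permits cataract surgery in the study eye without restriction by arm.

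**The concern.** A rate labelled intraocular inflammation will be read as inflammation inside the eye. Two of the listed terms describe a surgical wound. Implant insertion involves a scleral incision and a conjunctival peritomy (Protocol 5.1.3.2 to 5.1.3.4 and 5.1.3.7). Conjunctival, bleb or dislocation repair can reopen the site (Protocol 5.1.5.5, 5.1.5.6 and 5.1.5.8). An implant patient with an inflamed conjunctival wound and no cells or flare would count as an IOI case. The intravitreal arm has no counterpart in its study treatment.

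The second issue concerns the split. A site that finds cells in the anterior chamber and the vitreous, and follows the protocol, reports iridocyclitis. The SAP then counts that event as anterior. Vitreous cells alone, reported as vitritis, count as intermediate. The more extensive finding is thus placed in the anterior group. Because only one term goes in the event field, the vitreous component of that event need not appear anywhere else in the split.

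Intraocular inflammation is a named risk of ranibizumab injection (Protocol 5.1.2.3), so both the arm-level rate and the anatomical pattern matter for the safety account.

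**Working it through.** The documents state no IOI count, rate or power figure, so there is nothing to reproduce. The check is a comparison of texts plus count arithmetic.

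**1. Wound terms and the total rate**

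Inputs:
- 418 patients enrolled (SAP 2.2), randomized 3:2 (SAP 3.1). Actual arm totals are not given.
- Implant arm if exactly 3:2: 418 × 0.6 = 250.8, about 251. Intravitreal arm: 418 × 0.4 = 167.2, about 167.
- k, the number of implant patients whose **only** IOI term is incision site inflammation or inflammation of wound. This is an assumption, varied from 0 to 10.

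Taking the rate as the proportion of patients with at least one listed term, the over-count in percentage points is 100 × k / 250.8.

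| k | Over-count in implant-arm rate (points) |
|---|---|
| 0 | 0 |
| 1 | 0.4 |
| 3 | 1.2 |
| 5 | 2.0 |
| 10 | 4.0 |

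Patients who also have another listed term contribute nothing to k. Any intravitreal patient with wound inflammation after cataract surgery would raise that arm's rate as well, so the effect on the difference between arms could be smaller than the table shows.

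**2. Iridocyclitis and the split**

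| Finding | Term under Protocol 5.3.5 | SAP 4.7.1 group |
|---|---|---|
| Anterior chamber cells | Iritis | Anterior |
| Vitreous cells | Vitritis | Intermediate |
| Cells in both | Iridocyclitis | Anterior |

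Moving a term between groups leaves the total unchanged. With invented counts of 10 anterior (5 of them iridocyclitis), 4 intermediate, 1 posterior and 2 not otherwise specified, the total is 10 + 4 + 1 + 2 = 17. With iridocyclitis in its own row it is 5 + 5 + 4 + 1 + 2 = 17.

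**3. Do the two issues interact?**

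The wound terms sit in the not-otherwise-specified group. They affect that group and the total, but not the anterior, intermediate or posterior counts. The iridocyclitis placement affects only the anatomical rows. Neither offsets the other.

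**The case against.** The case for leaving the text alone has several parts.

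- **The analysis is descriptive and compares treatments as delivered.** SAP 4.7 plans mainly descriptive summaries. The safety objective concerns ranibizumab given through the implant, and Protocol 5.1.2.3 accepts that intraocular inflammation can arise "or in response to the invasive nature of the procedure". All of this stands, and any over-count goes against the implant arm. But a procedural cause does not make an external wound intraocular, and a safety rate should mean what its label says.
- **The information is available elsewhere.** Ocular adverse events are tabulated by preferred term (Protocol 6.5.1) and slit lamp inflammation by grade (SAP 4.7.5). This limits the harm. However, term counts do not show how many patients qualify for IOI on a wound term alone, and the slit lamp table does not correct the adverse event rate. The 37-day onset split in SAP 4.7.1 is specified for study-eye ocular events and ocular events of special interest. It is not specified for the IOI composite, and later repair surgery would fall after day 37.
- **The grouping follows a cited nomenclature, and Protocol 5.3.5 governs reporting rather than analysis.** Whether that nomenclature places iridocyclitis under anterior uveitis cannot be checked from the documents. Even if it does, sites were told to apply the protocol's definition, so the reported term carries the protocol's meaning.
- **The definition is already in use.** SAP Version 3 was written after the Primary and Update CSRs. Replacing the definition now would be a change made after results. This stands, and it argues for adding a summary, not for substituting one.

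A reader might go further and infer that only the implant arm can have these events, that the arm comparison and the split are both wrong, or that two opposing errors make the table unreadable. The documents do not support this. Cataract surgery is permitted in both arms, and post procedural inflammation can follow an injection. No count shows that the comparison is in fact distorted. The two issues act on different rows.

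**Conclusion.** The concern holds in a limited form. As written, the IOI definition can over-count the implant arm through two terms that do not show inflammation inside the eye and that relate to an incision only that arm receives as study treatment. The amount is unknown and may be zero. It is 0 to 4 percentage points if 0 to 10 of about 251 implant patients qualify on those terms alone. That range rests on an assumed patient count and an exact 3:2 split.

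Separately, the anatomical split can understate vitreous involvement, because the protocol's reporting term for cells in both compartments is counted as anterior. The total IOI rate is unaffected by this.

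Both are matters of labelling and interpretation in a descriptive safety summary. Neither bears on the efficacy conclusions or on any planned test.

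**What to change.** In SAP 4.7.1:

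1. Keep the Primary CSR definition and report it, for continuity.
2. Add the total IOI rate by arm excluding incision site inflammation and inflammation of wound, and show those two terms together in their own row.
3. Show iridocyclitis in its own 'anterior plus vitreous' row, with a footnote citing Protocol 5.3.5. Adding this row back to the anterior row recovers the Primary CSR grouping.

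Leave post procedural inflammation and eye inflammation as they are. Requiring slit lamp confirmation for these unsited terms may look natural, but it would create unequal ascertainment. The implant arm has scheduled slit lamp examinations on Days 2 and 7 (Protocol Appendix 1, Table 1), whereas the intravitreal arm's first scheduled post-treatment examination is at Week 4 (Protocol Appendix 2, Table 1). Unscheduled visits would only partly close that gap.

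The cost is a short wording change and table programming on data already collected. The downside is one extra summary specified after the Primary CSR, and it should be labelled as such.
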